## 4.1 PRIMARY OBJECTIVES

- To evaluate Overall Response Rate (ORR) after a maximum of 18 months treatment in patients with advanced melanoma receiving IMM-101 + nivolumab. ORR in both previously untreated patients (cohort A) and in patients whose disease has progressed during PD-1 blockade (cohort B) will be evaluated using RECIST 1.1. ORR will also be assessed for subgroups based on PD-L1 status (positive or negative/undetermined) in cohort A patients.
- To evaluate the safety and tolerability of the combination of IMM-101 + nivolumab in patients with advanced melanoma by examining the profile of adverse events experienced.

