## Efficacy is measured by:

• Overall Response Rate (ORR), calculated from the Best Overall Response (BOR) of patients as assessed by RECIST 1.1. ORR is defined as the number of patients with a BOR of CR or PR divided by the number of enrolled patients in each cohort of the study. The BOR is determined once all the data for the subject is known. It is defined as the best response designation, as determined by the Investigator, recorded from the first post-baseline scan until and including the last scan prior to, or at, the end of study treatment for each patient on study. For any patients in cohort B of the study who change treatment on study to IMM-101 + ipilimumab, BOR will be assessed only until the point of this change in therapy.

In addition, for patients in cohort A, BOR and ORR are assessed after all patients have had the opportunity for 1 year on study (using data from scans obtained up to this time point for each patient), and again at the end of study or when all patients in this cohort have withdrawn, if this is sooner. For patients in cohort B, BOR and ORR are assessed after all patients have had the opportunity for 6 months on study (using data from scans obtained up to this time point for each patient, or until the point of change of therapy to IMM-101 + ipilimumab where applicable) and again at the end of study or when all patients in this cohort have withdrawn, if this is sooner. ORR and BOR will also be assessed for subgroups based on PD-L1 status (positive or negative/undetermined) for cohort A patients at the end of the study.

Evaluation of the primary endpoints will take place when all patients have had the opportunity for a maximum of 18 months study treatment in each cohort. An interim data review on each respective cohort will be conducted after all cohort B patients have had 6 months on study (cohort B), and when all cohort A patients have had the opportunity for 12 months on study.

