If imaging shows a complete response (CR) or partial response (PR), according to the rules in 8.5.3.1, tumour imaging should be repeated at least 4 weeks later to confirm response, per RECIST 1.1 recommendations. The results of both the first (original) scan showing a CR or PR according to the rules in 8.5.3.1 as well as those of the confirmatory scan should be entered into the eCRF. The values for the original scan should not be amended in the eCRF even if the confirmatory scan does not confirm the results of the original scan. The confirmed response is used for the calculation of BOR (and hence the primary endpoint of ORR). However, BOR and hence ORR, using unconfirmed responses will also be calculated for comparability with published data. Following a confirmatory scan, the patient will then return to regular scheduled imaging every 8 weeks relative to the Week 12 scan (Cohort A) or Week 6 scan (Cohort B) and 12 weekly for patients still on study after Week 52. Patients who obtain a confirmation scan do not need to undergo scheduled imaging assessment 4 weeks later (e.g., if a patient obtains a scan at Week 16 to confirm a Week 12 response, their next scheduled scan would not be performed until Week 28, with no scan at Week 20). Once a response is confirmed, repeat scans are not required to confirm subsequent instances of the same response.

Page 59 of 98

If imaging shows PD, it is at the discretion of the investigator whether to continue or stop study treatment (i.e. both IMM-101 and nivolumab/ipilimumab) recognising that some patients with advanced melanoma can have a transient tumour flare in the first few months after start of immunotherapy with subsequent disease response. This decision will be based on clinical judgment but to continue treatment on study after disease progression is identified by a scan, the patient should have:

- Absence of clinical symptoms and signs indicating disease progression (including worsening of laboratory values)
- No decline in performance status
- Absence of disease symptoms indicative of requiring alternative treatment
- No clinically relevant adverse effects related to study treatment

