# **10.1.2 Best Overall Response**

Best Overall Response (CR, PR, SD or PD) is determined as the best response designation, recorded from the first post-screening scan until and including the last imaging assessment on study for each patient. All scans will be evaluated for overall response and BOR will be calculated based on overall response designations determined by the Investigator, from all scan assessments. However, for any patients in cohort B who change treatment on study to IMM-101 + ipilimumab, BOR will be assessed both before a change to ipilimumab for patients to whom this applies (for evaluation of ORR), and also from all tumour assessments on study.

BOR according to both RECIST 1.1 criteria and irRC criteria will be determined.

For cohort A, BOR will be assessed at the time point when all patients have had the opportunity for 12 months on study (RECIST 1.1 only), and again at the end of the study. For the first assessment, the BOR will be the best response designation, as determined by the Investigator, recorded from the first post-screening scan until the last scan prior to or at the 12 month time point for each patient on study.

For cohort B, BOR will be assessed at the time point when all patients have had the opportunity for 6 months on study (RECIST 1.1 only) and again at the end of study or when all patients in this cohort have withdrawn if this is sooner. For the first assessment, the BOR will be the best response designation, as determined by the Investigator, recorded from the first post-screening scan until the last scan prior to or at the 6 month time point for each patient on study. For any patients in cohort B of the study who change treatment on study to IMM-101 + ipilimumab, BOR will be assessed both before a change to ipilimumab for patients to whom this applies (for evaluation of ORR), and also from all tumour assessments on study.

In this study, the minimum scan time from Screening for determination of SD will be 9 weeks.

Confirmed response is used for calculation of BOR (Section 8.5.3.10); however unconfirmed results will also be analysed and corresponding BOR and ORR reported for comparability with published data.

Page 74 of 98

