#### 10.4 PD-L1 STATUS

The endpoint of BOR will be assessed for subgroups based on PD-L1 status (positive and negative/indeterminate) for subjects in cohort A of the study only. The following definitions apply:

PD-L1 positive:  $\geq 5\%$  tumour cell membrane staining in a minimum of a hundred evaluable tumour cells.

PD-L1 negative: < 5% tumour cell membrane staining in a minimum of a hundred evaluable tumour cells).

Page 75 of 98

PD-L1 indeterminate: tumour cell membrane scoring hampered by high cytoplasmic staining or melanin content.

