### 11.7.2 Subgroups For Analysis

Subgroups of patients in both cohorts will be defined based on BRAF status (Wild type, Mutant), Disease stage (M staging:- M1c (if Cohort B, combined with M1d), M0 combined with M1a and M1b) and LDH at baseline ( $\leq$  ULN, > ULN categorisation). Subgroups of patients in cohort A will be defined based on PD-L1 status (PD-L1 positive and PD-L1 negative/indeterminate) at Screening. These subgroups will be summarised for the primary endpoint of ORR (RECIST 1.1) at the end of the study.

A subgroup of patients in cohort B will be defined as those cohort B patients who receive IMM-101 + ipilimumab as subsequent treatment (Cohort B IMM-101 + ipilimumab subgroup). This subgroup will be assessed for the primary safety endpoints of the incidence and frequency of adverse events, serious adverse events, treatment-related adverse events and immune-related adverse events (as listed in the SmPC for ipilimumab) experienced following the start of ipilimumab treatment up to the end of the study.

All subgroups will be summarised provided the respective subgroup size is at least 33% of the total size of the ITT set for cohort A and in cohort B, if at least 50% of the cohort B subjects are in the respective subgroup.

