2.2 Study Endpoints

2.2.1 Primary Endpoints

The primary efficacy endpoint of the study is the ORR calculated from the BOR of patients as assessed by RECIST 1.1. ORR will be assessed at the end of study or when all patients have withdrawn, if this is sooner. For cohort B, ORR will apply to BOR from tumour assessments during IMM-101 + nivolumab treatment only. ORR and BOR will also be assessed for subgroups based on PD-L1 status (positive or negative/undetermined) in cohort A patients.

The primary safety endpoint of the study is the incidence, frequency and severity of AEs, serious adverse events (SAEs), treatment related AEs, immune-related AEs, Grade 3 and above AEs and AEs leading to IMM-101 discontinuation or study withdrawal experienced during treatment with IMM-101 + nivolumab for both cohorts.

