Listings of the baseline and follow-up target lesions will be provided. These listings will be presented for both assessment using RECIST 1.1 and repeated for assessment using irRC. The response assessment for both RECIST 1.1 and irRC will also be listed. Listings of non-target lesions at baseline and follow-up will be presented. New lesions found after baseline will be listed and the assessments of these previously reported new lesions will also be listed.

A BOR listing will present the responses derived using RECIST 1.1 including confirmed responses only, unconfirmed responses, all responses (confirmed or unconfirmed) up until progression, confirmed responses at interim assessment, and all responses (confirmed or unconfirmed) including those after a treatment change in Cohort B. The BOR derived using irRC will also be presented.

Sensitivity Analysis

Two sensitivity analyses will be performed for comparability with published data:

1. The summary table will be repeated with BOR assessed using confirmed or unconfirmed responses.
2. The summary table will be repeated with BOR assessed using confirmed or unconfirmed responses up until disease progression (i.e. excluding any PR and CR responses following a PD response).

Unconfirmed responses do not need to follow Table 3 of RECIST 1.1. Instead, the BOR is defined as the best overall response during the defined period and does not need to be confirmed at a subsequent timepoint, hence overall responses whether confirmed or not are assessed in the evaluation of BOR.

Exploratory Analysis

Further summaries by subgroup will be provided where BOR is assessed using unconfirmed responses.

The summary table described above will be repeated for each of the following subgroups:

- PD-L1 status at screening (positive/negative or indeterminate) for Cohort A only.
- M staging at screening (M1c and M1d/M0, M1a and M1b) for Cohort A only.
- BRAF status at screening (wild type/mutant) for Cohort A only.
- LDH at baseline (\leq upper limit of normal/ $>$ upper limit of normal) for Cohort A and B.

The criteria for presentation of these outputs are described in Section 5.2.8.

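### SAP 5.13.1 plans the Cohort A PD-L1 subgroup ORR, part of the primary objective, only on unconfirmed responses, while the primary ORR uses confirmed ones

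*SAP*

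**What the plan says.** **Status of the PD-L1 subgroup.** Protocol 4.1 includes it in the first primary objective: "ORR will also be assessed for subgroups based on PD-L1 status (positive or negative/undetermined) in cohort A patients". Protocol 5.2.1 repeats it in the primary efficacy endpoint: "ORR and BOR will also be assessed for subgroups based on PD-L1 status (positive or negative/undetermined) for cohort A patients". SAP 2.1.1 and 2.2.1 carry both statements over; the latter reads "ORR and BOR will also be assessed for subgroups based on PD-L1 status (positive or negative/undetermined) in cohort A patients".

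**Endpoint for the subgroups.** Protocol 11.7.2 defines subgroups by BRAF status, M stage, LDH and, in Cohort A, PD-L1, and says: "These subgroups will be summarised for the primary endpoint of ORR (RECIST 1.1) at the end of the study".

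**Response basis of the primary ORR.** Protocol 8.5.1 says: "The confirmed response is used for the calculation of BOR (and hence the primary endpoint of ORR"). Protocol 10.1.2 and 11.1.5 and the primary analysis in SAP 5.13.1 agree. Protocol 11.1.5 gives results on unconfirmed responses the role of a sensitivity analysis.

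**Response basis of the subgroup tables.** SAP 5.13.1, under its exploratory heading, says: "Further summaries by subgroup will be provided where BOR is assessed using unconfirmed responses". The list that follows includes PD-L1 for Cohort A. SAP 5.2.8 leaves the use of subgroups to the individual sections, and no other section specifies a PD-L1 table for ORR.

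**The concern.** The protocol requires a Cohort A tumour sample because the study needs to relate efficacy to PD-L1 status (Protocol 5.1). On the SAP text, that relation would be tabulated only on a definition that the protocol reserves for sensitivity analysis. A reader who sets the PD-L1 table beside the headline ORR would be comparing two definitions of response, and the subgroup responders need not add up to the headline count.

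Response is judged by the investigator in an open-label, non-randomised study, so the confirmatory scan is a real safeguard. Dropping it for this component alone needs a stated reason. Protocol 11.6 asks for departures from the planned analysis to be both documented and justified. The SAP states the basis openly but gives no reason. In SAP Section 6 the only subgroup entry concerns subgroup size.

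**Working it through.** The plan gives no sample size calculation, power or significance level, so it has no figure of its own to reproduce. The check compares the texts and then sizes the possible gap.

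**Step 1: which definition applies.**

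| Item | Source | Basis |
|---|---|---|
| Primary ORR | Protocol 8.5.1, 10.1.2, 11.1.5; SAP 5.13.1 | Confirmed |
| Subgroup ORR, including PD-L1 | Protocol 11.7.2, by reference to the primary ORR | Confirmed |
| Subgroup ORR, including PD-L1 | SAP 5.13.1, exploratory part | Unconfirmed |

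Protocol 10.4 is less specific: "The endpoint of BOR will be assessed for subgroups based on PD-L1 status". It does not mention confirmation, but Protocol 10.1.2 derives BOR from confirmed responses, so it gives no independent support for an unconfirmed basis.

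**Step 2: direction.** Under the unconfirmed definition in SAP 5.13.1, a CR or PR counts whether or not a later scan confirms it. Every confirmed responder is therefore also an unconfirmed responder, and in any subgroup unconfirmed ORR ≥ confirmed ORR.

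**Step 3: size per patient.** One never-confirmed responder shifts a subgroup of n patients by 100/n percentage points. SAP 5.2.8 requires a Cohort A subgroup to hold at least 33% of enrolled patients: 0.33 × 18 = 5.94, so at least 6. SAP Section 4 gives 11 Cohort A patients at the suspension of recruitment. If the cohort stayed there, 0.33 × 11 = 3.63, so at least 4.

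| Cohort A size | n in PD-L1 level | Shift (points) |
|---|---|---|
| 18 | 6 | 16.7 |
| 18 | 9 | 11.1 |
| 18 | 12 | 8.3 |
| 11 | 4 | 25.0 |
| 11 | 5 | 20.0 |
| 11 | 6 | 16.7 |
| 11 | 7 | 14.3 |

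In the full cohort of 18 the same patient shifts ORR by 100/18 = 5.6 points.

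**Step 4: illustration.** The counts here are assumptions, not figures from the documents. Take 18 patients split 9/9 by PD-L1, with 5 responders among the positive and 3 among the negative or indeterminate. One of the positive responses is never confirmed. Intervals are exact (Clopper-Pearson): for x of n, the lower limit is the 0.025 quantile of Beta(x, n − x + 1) and the upper limit is the 0.975 quantile of Beta(x + 1, n − x).

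| Table | Result | Exact 95% CI |
|---|---|---|
| Headline ORR, confirmed | 7/18 = 38.9% | 17.3 to 64.3 |
| Whole cohort, unconfirmed (sensitivity analysis 1) | 8/18 = 44.4% | 21.5 to 69.2 |
| PD-L1 positive, as the SAP plans it | 5/9 = 55.6% | 21.2 to 86.3 |
| PD-L1 negative or indeterminate, as the SAP plans it | 3/9 = 33.3% | 7.5 to 70.1 |
| PD-L1 positive, primary definition | 4/9 = 44.4% | 13.7 to 78.8 |

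The planned subgroup table shows 5 + 3 = 8 responders against 7 in the headline.

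**The case against.** The strongest case on the other side has five parts.

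- **A reason can be inferred.** Protocol 8.5.1 and 10.1.2 say unconfirmed results are calculated so that they can be compared with published results, and that comparison is part of the study's purpose. This stands as a reason to have an unconfirmed table. But the protocol adds the unconfirmed results to the confirmed ones and does not substitute them. In SAP 5.13.1 the reason is attached to the two sensitivity analyses, not to the subgroups.
- **The justification could come later.** Protocol 11.6 also accepts the clinical study report as the place for it. That is right, so the supportable statement is that the SAP itself gives no justification. The mismatch with Protocol 11.7.2 remains.
- **A matching total is planned.** The subgroup tables share the basis of sensitivity analysis 1 and should add up to it. In the illustration that total is 8/18. This stands and softens the reconciliation problem, but the headline ORR itself would still not be tabulated by PD-L1 status.
- **The consequence is limited.** There is no hypothesis testing, the intervals are wide on either basis, and the gap vanishes if every response is confirmed. Confirmed BOR and the PD-L1 assessment are both listed per subject, so the figure could be rebuilt by hand. All of this stands and limits the weight of the point. It does not make the text consistent.
- **The table shells are a separate document and may include a confirmed table.** They were not available, so the finding is limited to the SAP text. If such a table exists, SAP 5.13.1 should name it.

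**Conclusion.** The concern holds. As written, SAP 5.13.1 tabulates a component of the primary objective and endpoint on a definition that differs from the primary ORR and can only equal or raise the response rate, without a reason in the SAP. The effect is 1/n per never-confirmed responder: 8.3 to 16.7 points for PD-L1 levels of 6 to 12 patients out of 18, and 14.3 to 25.0 points for levels of 4 to 7 out of 11. How many such patients there will be is unknown, because the documents give neither a confirmation rate nor a PD-L1 split. The matter is one of consistency and interpretation, not of error control. It should be corrected because in a descriptive study the estimate is the result. The same unconfirmed basis applies to the M stage, BRAF and LDH subgroups, but only PD-L1 is named in the primary objective.

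**What to change.** In SAP 5.13.1, specify the subgroup ORR tables, at least PD-L1 in Cohort A, on confirmed BOR with exact 95% confidence intervals as the main version. Keep the unconfirmed version beside it as a sensitivity analysis, with the published-data comparison given as its reason and a note that it adds up to sensitivity analysis 1. If any subgroup is to stay on unconfirmed BOR only, record and justify that in SAP Section 6.

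The cost is one extra table for PD-L1, or a few if all subgroups are covered, and possibly a line in Section 6. Confirmed BOR is already derived and listed per subject, so no new data or derivation is needed. The drawback is two versions of a small table with wide intervals.

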5.13.2 Secondary Endpoints

5.13.2.1 PFS Assessed by RECIST 1.1 for Cohorts A and B

PFS will be analysed using the ITT set and analysis will be repeated for the PPS for Cohort A only.

PFS is defined in months as the time between Visit 1 and the first confirmation of progression using RECIST 1.1, or death from any cause (whichever occurs first) (date

of first progression or death – date of Visit 1 + 1). Progression is determined by the investigator using the CT or MRI scan (scheduled or unscheduled) or death due to any cause. Subjects who die without reported progression will be considered to have progressed on the date of their death.

The following censoring rules will apply:

- Subjects who did not progress or die will be right censored on the date of their last evaluable tumour assessment.
- Subjects who did not have any on-study tumour assessments (scans) and did not die will be right censored on their date of first post-Screening visit. Note that this definition is consistent with that used for [Checkmate 067](#)².
- Subjects who remain on study following radiotherapy or other prohibited treatment will be censored at their last scan assessment prior to the intervention therapy.
- Subjects in Cohort B who change therapy to IMM-101 + ipilimumab without documented progression by RECIST 1.1 will be censored at the date of their last evaluable tumour assessment prior to this change in therapy.

Summaries of PFS

Descriptive statistics will be presented for PFS. The number and percentage of subjects that are censored will be summarised, along with KM estimates for the 25th, 50th and 75th percentiles of PFS and corresponding 95% CIs. PFS will also be presented graphically using a KM plot. The proportion of subjects who have not progressed or died at three monthly intervals will also be presented.

A time to event listing will present the milestones required for calculation of each time to event efficacy parameter.

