# 8.5.3.10 Confirmatory Scans (RECIST 1.1 and irRC)

Confirmation of response (CR and PR) is required for RECIST 1.1 with the confirmatory scan being carried out at least 4 weeks after the scan from which a response was seen. Patients will then return to regular scheduled imaging every 8 weeks relative to the Week 12 scan (Cohort A) or Week 6 scan (Cohort B) and 12 weekly for patients still on study after Week 52. Patients who obtain a confirmation scan do not need to undergo scheduled imaging assessment 4 weeks later (e.g., if a patient obtains a scan at Week 16 to confirm a Week 12 response, their next scheduled scan would not be performed until Week 28, with no scan at Week 20).

Once a response is confirmed, repeat scans are not required to confirm subsequent instances of the same response.

Confirmatory scans for responses by irRC may be carried out at the discretion of the Investigator to assist in managing treatment on study.

If imaging shows PD, it is at the discretion of the Investigator whether to keep a patient on study treatment or to stop study treatment until imaging is repeated approximately 4 weeks later in order to confirm PD, per irRC recommendations.

If repeat scans confirm PD, then progression should be declared using the date of the initial scan. If repeat scans do not confirm PD, then the subject is considered not to have progressive disease per irRC.

If a confirmatory assessment is non-evaluable but the subsequent scan maintains the same response/progression, the response/progression can be considered confirmed (eg PR-NE-PR).

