### 10.2 PROGRESSION FREE SURVIVAL (PFS)

PFS is defined as the time between the date of the first post-Screening visit (Week 0, Visit 1) and the first date of documented progression, according to RECIST 1.1, as determined by the Investigator from CT/MRI scans, or death due to any cause, whichever occurs first.

Patients who die without a reported progression will be considered to have progressed on the date of their death. Subjects who did not progress or die will be censored on the date of their last evaluable tumour assessment. Subjects who did not have any on study tumour assessments (scans) and did not die will be censored on the date of first post-Screening visit. Subjects in cohort B who change therapy on study to IMM-101 + ipilimumab without documented progression by RECIST 1.1 will be censored at the date of their last evaluable tumour assessment (scan) prior to this change in therapy.

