5.13 EFFICACY EVALUATION

5.13.1 Primary Endpoint

The primary endpoint will be analysed using the ITT set and repeated for the PPS for Cohort A only.

Primary Analysis

The primary efficacy endpoint of the study is the ORR calculated from the BOR of subjects as assessed by RECIST 1.1.

The investigator response will be entered into the Response Assessment (RECIST 1.1) page of the electronic Case Report Form (eCRF) at each scan assessment to be used in the derivation of BOR.

A confirmed response will be used in the derivation of BOR. A confirmed response is defined as a response obtained from a scan repeated at least 4 weeks following a scan with designation of complete response (CR) or partial response (PR), as defined using Table 3 of RECIST 1.1. In addition, the following approaches will be taken:

- Where a confirmatory assessment is non-evaluable (NE) but the subsequent scan maintains the same response/progression, the response/progression will be considered confirmed (e.g. PR-NE-PR).
- Subjects without a confirmed response of CR or PR will have their next best response (stable disease (SD) or otherwise progressive disease (PD)) assigned as their BOR.
- Subjects without a BOR assessment, such as those with no post-baseline responses or only NE responses, will be assumed to have a BOR of PD using a worst-case approach.

For Cohort A, BOR is defined as the best confirmed response designation, recorded from the first post-baseline scan until and including the last scan on study for each subject.

For Cohort B, BOR is defined as the best confirmed response designation, recorded from the first post-baseline scan until and including the last scan on study for each subject for those receiving IMM-101 and nivolumab, or the last scan performed prior to treatment with ipilimumab. No scan performed once ipilimumab treatment commences will be included.

All scans within these periods, whether scheduled or unscheduled, will be evaluated for overall response.

ORR is calculated as the number of subjects with a BOR of confirmed CR or PR divided by the number of subjects in the analysis set. ORR is calculated for each cohort separately.

Summaries of BOR (best confirmed overall response designation)

The BOR will be summarised for each cohort. The ORR and accompanying exact binomial 95% confidence intervals (CI) will also be presented.

Listings of lesions assessments and BOR

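### The wording of the SAP's PFS definition ends at confirmed progression, which conflicts with the protocol and with the SAP's own formula

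*SAP*

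**What the plan says.** The SAP's definition (5.13.2.1) reads: "PFS is defined in months as the time between Visit 1 and the first confirmation of progression using RECIST 1.1", or death if sooner. The bracketed formula that completes the sentence takes the date "of first progression or death – date of Visit 1 + 1". The section continues: "Progression is determined by the investigator using the CT or MRI scan (scheduled or unscheduled) or death due to any cause".

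The censoring rules that follow do not mention confirmation. The general rule is "Subjects who did not progress or die will be right censored on the date of their last evaluable tumour assessment". The Cohort B rule is "Subjects in Cohort B who change therapy to IMM-101 + ipilimumab without documented progression by RECIST 1.1 will be censored", at the last evaluable scan before the switch.

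Protocol 10.2 ends PFS at "the first date of documented progression, according to RECIST 1.1, as determined by the Investigator from CT/MRI scans", or at death from any cause. Protocol 5.2.2 says the same. Protocol 8.5.3.10 requires confirmation under RECIST 1.1 for CR and PR only. It describes repeat imaging about 4 weeks later to confirm PD as an irRC recommendation, and leaves to the Investigator whether treatment continues or stops meanwhile. On dating it says: "If repeat scans confirm PD, then progression should be declared using the date of the initial scan".

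SAP section 6 lists five changes or clarifications to the protocol's planned analysis. None concerns PFS.

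**The concern.** In this SAP, confirmation has a technical meaning for tumour assessments. Section 5.13.1 defines a confirmed response by a repeat scan at least 4 weeks after a scan showing CR or PR. A bullet there on non-evaluable confirmatory scans extends the term to PD: "the response/progression will be considered confirmed (e.g. PR-NE-PR"). An analyst who meets the same term in the PFS definition could reasonably read it as a repeat-scan requirement. The protocol sets no such requirement for RECIST 1.1 progression.

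The trial is likely to produce patients in whom the two readings differ:

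- Treatment beyond RECIST progression is allowed in both cohorts (protocol 5.1 and 7.5).
- Unscheduled scans are allowed in order to confirm progression (protocol 5.1).
- Protocol 5.3 anticipates early tumour flare with later response.
- Protocol 11.1.5 plans a sensitivity analysis in case PR or CR follows progression.

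What is at stake is which scans count as PFS events and, possibly, their dates. PFS is secondary and descriptive. However, protocol section 4 and SAP 2.1 say that efficacy will be compared with published nivolumab data, and SAP 5.13.2.1 itself aligns one censoring rule with CheckMate 067. A different event rule would weaken that comparison.

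**Working it through.** The documents give no sample size, power or event figure that rests on this definition, so there is no stated figure to reproduce. The check is a comparison of texts, followed by an illustration of scale.

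**1. Event definition, place by place**

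- Protocol 5.2.2 and 10.2: first documented RECIST 1.1 progression, no confirmation.
- Protocol 8.5.3.10: RECIST 1.1 confirmation for CR and PR; PD confirmation tied to irRC; a confirmed PD keeps its initial date.
- SAP 5.13.2.1, words: first confirmation of RECIST 1.1 progression.
- SAP 5.13.2.1, formula: date of first progression.
- SAP 5.13.2.1, remaining text: progression that is reported, documented or determined by the investigator. There is no repeat-scan rule, no confirmation window and no rule that censors an unconfirmed PD.
- SAP 5.13.3.2 (duration of response): documented PD.

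The words of the definition are the only item in this list that ties a RECIST 1.1 progression event to confirmation.

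**2. What the formula settles**

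The formula settles the date: it is that of the first progression, so the shift is 0 months. It does not say whether a PD that is never repeated, or that is followed by response, counts as a progression at all.

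**3. Three patients under the two readings**

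- *PD, no repeat scan.* Protocol: event at that scan. Words read as a repeat-scan requirement: no event unless the patient dies or has a later confirmed PD.
- *PD, then response (flare).* Protocol: event at the first PD. Words: that PD is never confirmed, so no event until a later confirmed PD or death.
- *PD, confirmed at a repeat scan.* Protocol: event at the first PD. Words: also an event, and late only if dated at the repeat scan.

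**4. Scale of late dating, if it happened (illustration)**

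The PFS formula gives days + 1. I assume the SAP's month divisor of 30.4375 (used in 5.7.3 and 5.12), since 5.13.2.1 states none. First scans are at Week 12 (Cohort A) and Week 6 (Cohort B), per protocol 5.1.

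- Cohort A, PD at Week 12: (84 + 1)/30.4375 = 2.79 months. Dated at Week 16: (112 + 1)/30.4375 = 3.71.
- Cohort B, PD at Week 6: (42 + 1)/30.4375 = 1.41 months. Dated at Week 10: (70 + 1)/30.4375 = 2.33.
- Shift for a 4-week repeat: 28/30.4375 = 0.92 months.
- Shift if the next 8-weekly scan served: 56/30.4375 = 1.84 months.
- Shift for a 12-weekly scan after Week 52: 84/30.4375 = 2.76 months.

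**5. Scale of one uncounted event**

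At the planned enrolment, one patient is 1/18 = 5.6% of Cohort A or 1/8 = 12.5% of Cohort B. The documents do not say how many PDs would go unrepeated or unconfirmed, so no total can be given.

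**The case against.** A reader might infer that the SAP will date PFS events late and lose progressions that are not re-scanned. The documents do not support that as a stated consequence:

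- The formula in the same sentence uses first progression, so applied as written it moves nothing.
- The rest of the section speaks of documented or reported progression, sets no repeat scan, and censors only subjects who neither progressed nor died.
- Even a confirmed PD is dated at the initial scan under protocol 8.5.3.10. Late dating would contradict that rule as well as the SAP formula.
- An uncounted PD is not necessarily lost. Death from any cause is a PFS event and survival is followed to database lock, so in patients who die the event would be delayed.
- The SAP states that it is based on protocol Version 2 and lists its departures in section 6. The absence of PFS from that list suggests loose wording rather than an intended change.
- The bullet on non-evaluable scans in SAP 5.13.1 closely follows protocol 8.5.3.10 and governs BOR, so it is weak evidence of a PFS rule.
- The SAP plans a listing of the milestones behind each time-to-event endpoint, so a misapplied date would be visible.

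These points stand, and they limit the consequence to a conditional one. They do not remove the conflict. A definition whose words and formula disagree leaves the analyst to choose, and the formula does not decide whether an unrepeated or reversed PD is an event.

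**Conclusion.** The point holds as a conflict of wording. SAP 5.13.2.1 departs in words from the protocol's PFS endpoint and from its own formula, and section 6 does not declare the departure, although protocol 11.6 asks for deviations from the statistical plan to be documented and justified.

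The effect is zero if the formula is followed with any investigator-assessed RECIST 1.1 PD counted as progression. It arises only if the words are taken as a repeat-scan requirement. Unrepeated or unconfirmed PDs would then not be events until a later confirmed PD or death. If events were also dated at the repeat scan, a 4-week repeat would add about 0.9 months. Both effects lengthen PFS. The number of patients affected is unknown.

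This is worth correcting because the trial expects treatment beyond progression and flare, the cohorts are small, and the correction is nearly free. It does not bear on the primary endpoint or on any hypothesis test; none is planned.

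**What to change.** In SAP 5.13.2.1, replace the phrase that ends PFS at the first confirmation of progression with: *first documented progression per RECIST 1.1, dated at the first scan with investigator-assessed PD; no confirmatory scan is required*. The death component and the formula can stay as they are.

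No edit is needed in 5.13.3.2, which already uses documented PD. The bullet on non-evaluable scans in 5.13.1 should also stay, because changing it would create a new difference from protocol 8.5.3.10.

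The cost is SAP wording only. Protocol 5.3 already has the RECIST 1.1 assessment of every scan recorded in the eCRF, so no new data are required.
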